## 3.2 Exclusion Criteria

- 3.2.1 Patients who have had chemotherapy, radiotherapy, or major surgery within 4 weeks (6 weeks for nitrosoureas or mitomycin C) prior to entering the study.
- 3.2.2 Patients may not be receiving any agents not approved by the FDA within the past four weeks.
- 3.2.3 Patients with known brain metastases should be excluded from this clinical trial because of their poor prognosis and because they often develop progressive neurologic dysfunction that would confound the evaluation of neurologic and other adverse events.
- 3.2.4 Mean QTc >470 msec (with Bazett's correction) in screening electrocardiogram or history of familial long QT syndrome.
- 3.2.5 Greater than +1 proteinuria on two consecutive dipsticks taken no less than 1 week apart.
- 3.2.6 Uncontrolled intercurrent illness including, but not limited to hypertension, ongoing or active infection, symptomatic congestive heart failure, unstable angina pectoris, cardiac arrhythmia, or psychiatric illness/social situations that would limit compliance with study requirements.
- 3.2.7 HIV-positive patients on combination antiretroviral therapy are ineligible because of the potential for pharmacokinetic interactions with AZD2171.

#### 3.3 Inclusion of Women and Minorities

Men of all races and ethnic groups are eligible for this trial. Women are excluded by the nature of the disease.

## 3.4 Baseline evaluation

- 3.4.1 Imaging studies (baseline obtained within one month prior to enrollment): Technetium-99 Bone Scintigraphy, Chest X-ray, CT scan of chest, abdomen and pelvis.
- 3.4.2 Laboratory evaluation (baseline obtained within 16 days prior to enrollment)
  - 3.4.2.1 Hematological profile: CBC with differential and platelet count, PT, aPTT, fibrinogen.

- 3.4.2.2 Biochemical profile: electrolytes, BUN, creatinine, AST, ALT, total bilirubin, calcium, phosphorus, albumin, magnesium, uric acid, C-reactive protein, albumin, amylase, lipase, testosterone level, TSH, and troponin.
- 3.4.2.3 Tumor marker profile: PSA (baseline within 7 days prior to phosphatase (if PSA <4ng/mL, for research purposes only).
- 3.4.2.4 History and physical exam with vital signs.
- 3.4.3 Cardiac evaluation (baseline obtained within 16 days prior to enrollment)
  - 3.4.3.1 Electrocardiogram
  - 3.4.3.2 Laboratory evaluation troponin
  - 3.4.3.3 Echocardiogram

## 3.5 **REGISTRATION PROCEDURES**

- 3.5.1 Authorized staff must register an eligible candidate with NCI Central Registration Office (CRO) within 24 hours of signing consent. A registration Eligibility Checklist from the web site (http://camp.nci.nih.gov/ccr/welcome.htm) must be completed and faxed to [contact]. After confirmation of eligibility at Central Registration Office, CRO staff will call pharmacy to advise them of the acceptance of the patient on the protocol prior to the release of any investigational agents. Verification of Registration will be forwarded electronically via e-mail. Please note, it is very important for all registrars to acquire encrypted e-mail from NIH Help Desk, since the verification of registration includes patient's information. A recorder is available during non-working hours.
- 3.5.2 Off-Study Procedure: Authorized staff must notify Central Registration Office (CRO) when a patient is taken off-study. An off-study form from the web site (http://camp.nci.nih.gov/ccr/welcome.htm) main page must be completed and faxed to [contact].

#### 4. TREATMENT PLAN

#### 4.1 AZD2171-Prednisone Administration

At the outset of the study, the patient may be admitted to the inpatient service for a period of approximately 24 hours to complete research studies including biopsies and PK measurements. Otherwise, treatment will be administered on an outpatient basis. Reported adverse events (AEs) and potential risks are described in Section 6. Appropriate dose modifications for AZD2171 are described in Section 5. No investigational or commercial agents or therapies other than those described below may be administered with the intent to treat the patient's malignancy.

AZD2171 is supplied in a matched series of beige film-coated tablets containing 10 mg or 15 mg of AZD2171 free base. Patients are to swallow tablets to equal 20 mg without crushing with approximately 250ml (8 oz.) of water, once daily. AZD2171 tablets should be taken on an empty stomach, 1 hour before or 2 hours after meals. AZD2171 will be given as self-administered oral doses of 20 mg once daily continuously throughout the 28 day cycle.

Patients will be provided with a pill diary (Appendix B), instructed in its use, and asked to bring it with them to each appointment. A new copy of the Pill Diary will be given to patients whose dose is reduced due to adverse events. Pill counts will also be maintained be study personnel.

The combination of treatment of AZD with prednisone may help to alleviate some of the constitutional symptoms and allow us to maintain therapeutic dosing. All patients will receive Prednisone 10 mg orally daily and AZD2171 20 mg orally daily. Both drugs should be taken together in the morning. In addition, we will also check cortisol levels in patients who are not on steroids at the time of enrollment.

#### 4.2 General Concomitant Medication and Supportive Care Guidelines

4.2.1 Frequent blood pressure monitoring is important in patients receiving AZD2171. Experience to date

suggests that increases in blood pressure may occur following dosing with AZD2171 for a number of weeks and that these increases may occur relatively quickly. Patients will be provided with a blood pressure monitoring device and a log in which to record their twice-daily blood pressure readings (Appendix C). If two successive systolic readings are  $\geq$ 140 mmHg OR two successive diastolic readings are  $\geq$ 90 mmHg OR any combination of elevated systolic and diastolic blood pressure are observed, patients will be instructed to contact their physician as soon as possible. Patients should seek medical advice if their BP exceeds 180 mmHg (systolic) or 105 mmHg (diastolic) at any time and should also be encouraged to contact their physician if they are concerned about any symptoms that may be associated with high blood pressure (*e.g.*, headache). Section 5.1 includes specific guidelines on the management and, if appropriate, dose modifications for treatment-emergent hypertension.

4.2.2 Renal function (creatinine and urinary protein) should be frequently monitored as suggested by the pathologic changes noted in animal studies and evidence from studies of other antiangiogenic agents. Patients will have a monthly chemistry panel and urinalysis.

Proteinuria Value	Monitoring	Dose modification
>1+ (dipstick or equivalent routine laboratory analysis)	
 
Perform the following tests:
 
24-hour urine collection for total protein and creatinine
 
	See below.
	
 
microscopic examination of fresh urine
 
	
	
 
urine protein electrophoresis (at first occurrence of >1+ proteinuria only)
 
	
Based on results of the 24-hour	urine collection:	1
≤ 1g protein (24-hour collection)	Continue dipstick or equivalent routine laboratory analysis	Continue planned dose.
> 1g but ≤ 2g protein (24-hour collection)	Perform 24-hour urine collection (total protein, creatinine) prior to day 1 of each subsequent cycle of therapy (q4wk) until total protein is <500mg/24 hours.	Decrease one dose level; continue treatment.
> 2a protoin	Perform 24-hour urine collection (total protein, creatinine) weekly unitl proteinuria is <2g/24 hours.	Hold AZD2171. When protein is < 2g/24
> 2g protein (24-hour collection)		hours, resume treatment at one lower dose level.
	Perform 24-hour urine collection (total protein, creatinine) prior to day 1 of each subsequent cycle of therapy (q4wk).	Continue until patient is off study.

#### Management of Proteinuria

- 4.2.3 Because of the potential for myocardial injury with AZD2171, patients will undergo electrocardigram testing and measurement of serum of troponin levels at each clinic visit.
- 4.2.4 Because there is a potential for interaction of AZD2171 with other concomitantly administered drugs through the cytochrome P450 system, the case report form must capture the concurrent use of all other drugs, over-the-counter medications, or alternative therapies. The Principal Investigator should be alerted if the patient is taking any agent known to affect or with the potential to affect selected P450 isoenzymes; these agents/drugs should be documented along with any associated AEs that occur.
- 4.2.5 No premedications will be used with the initiation of therapy

- 4.2.6 Concurrent use of bisphosphonates will be allowed for patients with known bone metastases
- 4.2.7 Patients who require hematopoietic growth factor support (e.g. epogen, darbepoetin), NSAIDs and other maintenance medications prior to study entry will be allowed to continue their supportive therapies.

## 4.3 Duration of Therapy

In the absence of treatment delays due to adverse event(s), treatment may continue until one of the following criteria applies:

- Radiographic disease progression,
- Intercurrent illness that prevents further administration of treatment,
- Unacceptable adverse event(s),
- Patient decides to withdraw from the study, or
- General or specific changes in the patient's condition render the patient unacceptable for further treatment in the judgment of the investigator.
- Patients who meet the criteria for PSA progression (See Section 10.5) may continue on study unless they meet the above criteria.

## 4.4 Follow-up Criteria

All study subjects will be followed for overall survival only once active treatment has been completed (as indicated above).

Follow-up will be annual telephone contact to assess survival status. Every attempt will be made to contact patient/subject including: contacting referring physician, contacting emergency contact patient identified on admission, checking SSDI (Social Security Death Index) All attempts will be noted in the medical record.

## 4.5 Off-Study Criteria

- Discretion of the principle investigator
- Patient Choice
- Patient Death

#### 5. DOSING DELAYS/DOSE MODIFICATIONS

Toxicities will be described using CTCAE v3.0. The following adjustments will only apply if the toxicities reported are attributed by the investigators to be related to AZD2171 therapy.

AZD2171 should be held in patients with symptoms/signs suggestive of RPLS, pending work-up and management, including control of blood pressure. Cediranib should be discontinued upon diagnosis of RPLS. After Consultation with the principal investigator and the NCI, consideration of restarting the study may be evaluated in light of any clinical benefit.

For Grade 1 toxicity, treatment with AZD2171 need not be interrupted. For symptoms that last more than 7 days and have been found to be intolerable to the patient, the dose of AZD2171 may be reduced to 15mg/day.

For Grade 2 toxicity

For nausea, vomiting, and diarrhea, maintain dosing with symptomatic treatment. The dose of AZD2171 may be repeated if emesis occurs within 30 minutes of taking the tablets or all the tablets are seen in the emesis.

For persistant nausea, vomiting or diarrhea despite symptomatic treatment that remains unacceptable (intolerable) to the patient, reduce dose to 15 mg/day, as indicated in the table below.

For other grade 2 toxicities, the dose does not need to be reduced unless side effects become intolerable to the patient.

Patients with intolerable or limiting toxicity while taking 10 mg/day will be removed from study

For Grade 3 nonhematologic toxicity, or Grade 4 hematologic toxicity

Hold AZD2171 and reevaluate the patient at least weekly until toxicity improves to  $\leq$  Grade 1 or pretreatment baseline. Reduce dose of AZD2171 by one dose level, as indicated in the table below except for grade 3 hypertension (follow chart found below). Treatment will be discontinued in patients who experience toxicity  $\geq$  grade 3 or 4 that does not resolved to  $\leq$  grade 1 or baseline within 3 weeks. Hypophosphotemia, hypokalemia, and hypomagnesimia that can be corrected within 48 hours to grade 2 or less will not require a dose reduction.

Patients with intolerable or limiting toxicity while taking 10 mg/day will be removed from study

For Grade 4 non-hematologic toxicity

Patients who had clinical grade 4 non-hematologic toxicity (except pulmonary embolism without significant hypoxia and hemodynamic instability) will be taken off study permanently.

Dose level	AZD2171 Dose
-2	10 mg qd
-1	15 mg qd
1	20 mg qd

As this trial allows patients to receive treatment indefinitely, patients may have the doses of any or all drugs (AZD-2171 and prednisone) temporarily withheld (maximum of 21days at which time the patient will be taken off study), and potentially resume treatment as long as they do not fulfill the off-study criteria outlined in section 4.5.

## 5.1 Management of Hypertension

Increases in blood pressure and cases of hypertension have been associated with many drugs acting on the VEGF pathway. The proposed mechanism for this increase is through inhibition of VEGF-induced peripheral vasodilation. Hypertension following AZD2171 treatment has been seen in animal studies as well as clinical trials. Blood pressure will be measured by a health professional at the time of enrollment, and at each clinic visit. In addition, patients will be asked to monitor their blood pressure at home on a twice daily basis, consisting of a a morning resting blood pressure and an evening blood pressure, and to log blood pressure values in a blood pressure diary (Appendix C). Patients will be asked to call their research nurse with any abnormal values (CTCAE v3.0 Grade 1 or above) or if they experience new headache or dizziness.Specific guidance for management of this AE is provided below.

BP monitors for patients enrolled in the study may be ordered from

[name], MS AstraZeneca Pharamceuticals [name] [contact] [contact]

Grade (CTCAE v3.0)	Antihypertensive Therapy	Blood Pressure Monitoring	AZD2171 Dose		
1	None	Consider increased monitoring	No change		
2	Initiate monotherapy (suggest dihydropyridine calcium-channel blocker)	Increase frequency and monitor (by health professional) every 2 days until stabilized.	No change		
3	Add agent(s): Ca++ channel blocker (if not already used), K+ channel opener, beta- blocker, thiazide diuretic)	Increase frequency and monitor (by health professional) every 2 days until stabilized; continue q2d monitoring to stabilization after dosing restarted.	Hold dose until symptoms resolve and diastolic BP ≤100 mm Hg. Restart at same dose (investigator discretion).		
		diastolic BP not controlled to $\leq$ 100 mm Hg on nerapy when dose restarted			
4	Manage symptoms per local practice.	Continue frequent BP monitoring until stabilization.	Discontinue AZD2171*		
If patient is considered to be benefiting from AZD2171 treatment, dosing may continue at the next lower dose level provided the responsible study sponsor (DCTD, NCI) physician concurs after discussion of the case.					
CTCAE v3.0 hypertension grade definitions					
	Grade 1: asymptomatic, transient (<24 hours) increase by >20 mm Hg (diastolic) or to >150/100 if previously WNL; intervention not indicated Grade 2: recurrent or persistent (>24 hours) or symptomatic increase by >20 mm Hg				
	Grade 3: requiring more than one drug or more intensive therapy than previously Grade 4: life-threatening (e.g., hypertensive crisis)				

Notes:

- While patients are receiving treatment with AZD2171, the early initiation of antihypertensive treatment for grade 1 or 2 hypertension to minimize more severe or persistent hypertension is not considered a grade 3 adverse event.
- Decisions to hold or decrease the AZD2171 dose during treatment must be based on BP readings taken in the clinic by a medical professional.

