- 3.1.9 All patients who have not undergone bilateral surgical castration must continue suppression of testosterone production by appropriate usage of GnRH agonists or antagonists.
- 3.1.10 Patients must not have other invasive malignancies (within the past three years with the exception of non-melanoma skin cancers or non-invasive bladder cancer).
- 3.1.11 AZD2171 has been shown to terminate fetal development in the rat, as expected for a process dependent on VEGF signaling. Enrolled patients must agree to use adequate contraception (hormonal or barrier method of birth control; abstinence) prior to study entry, the duration of study participation and 3 months after the end of the treatment.
- 3.1.12 Ability to understand and the willingness to sign a written informed consent document.
- 3.1.13 Patients must have a blood pressure of <140/90 at the time of enrollment. Details of antihypertensive treatment, if required, will be left up to the primary care physician.

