## **INSTRUCTIONS TO THE PATIENT:**

- 1. Your blood pressure readings have two numbers. The first number is the pressure in your blood vessels during a heart beat (systolic), and the second number is the pressure in the vessels when the heart rests in between beats (diastolic). These numbers are usually written with a slash in between them (for example, normal blood pressure is 120/80).
- 2. Record the date, then record your blood pressure twice each day using a home blood pressure monitor:
  - each morning after sitting quietly for 30 minutes or reading (not while you are active: dressing, making breakfast, etc.)
    - each evening at bedtime or while you are relaxing during the evening
- 3. If you take your blood pressure at other times of the day, please record the numbers and time under "Other readings."
- 4. If your systolic pressure is greater than 150 or your diastolic blood pressure is greater than 90 twice in a row measured several hours apart, please contact your research nurse at NIH for instructions.
- 5. Patients should seek medical advice immediately if their BP exceeds 180 mmHg (systolic) or 105 mmHg (diastolic) at any time and should also be encouraged to contact their physician if they are concerned about any symptoms that may be associated with high blood pressure (*e.g.*, headache).
- 6. Please bring this form to every clinic visit or appointment.

Date	AM reading	PM reading	Other readings (include time of day)	Date	AM reading	PM reading	Other readings (include time of day)
	S	S			S	S	
	/	/			/	/	
	/	/			/	/	
	/	/			/	/	
	/	/			/	/	
	/	/			/	/	
	/	/			/	/	
	/	/			/	/	
	/	/			/	/	
	/	/			/	/	
	/	/			/	/	
	/	/			/	/	
	/	/			/	/	
	/	/			/	/	
	/	/			/	/	
	/	/			/	/	
	/	/			/	/	
Patient's	Patient's Signature: Date:						

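### The grade 3 hypertension restart condition has no systolic limit, and section 5 leaves unclear whether its general hold or the 5.1 chart governs

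*Protocol*

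**What the plan says.** **The chart.** Protocol section 5.1, grade 3 row, dose column: "Hold dose until symptoms resolve and diastolic BP ≤100 mm Hg. Restart at same dose (investigator discretion". The same row calls for added antihypertensive agents and for checks by a health professional every 2 days until the pressure is stable, continuing after restart.

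**The grade.** Section 5.1 defines grade 3 by treatment need, without a pressure value: "Grade 3: requiring more than one drug or more intensive therapy than previously".

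**The other limits.**
- Enrolment (3.1.13): "Patients must have a blood pressure of <140/90 at the time of enrollment".
- Home contact: section 4.2.1 uses two successive readings of systolic 140 or more, or diastolic 90 or more. Appendix C says "If your systolic pressure is greater than 150 or your diastolic blood pressure is greater than 90 twice in a row".
- Medical advice: section 4.2.1 says "Patients should seek medical advice if their BP exceeds 180 mmHg (systolic) or 105 mmHg (diastolic) at any time". Appendix C says "Patients should seek medical advice immediately if their BP exceeds 180 mmHg (systolic) or 105 mmHg (diastolic) at any time".

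**The general rule.** Section 5 holds AZD2171 for grade 3 nonhematologic toxicity until it falls to grade 1 or lower or to the pretreatment baseline. The next sentence lowers the dose by one level, excepts grade 3 hypertension and refers the reader to the chart. Treatment stops if recovery is not reached within 3 weeks. Section 5 separately caps any interruption at 21 days.

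**The concern.** The chart decides when a patient is exposed to the drug again after a severe toxicity that the protocol expects. For that decision it bounds diastolic pressure and leaves systolic pressure open, although systolic pressure counts at entry, at home and in the medical-advice limit.

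The protocol's own safety text shows what is at stake. Section 6.1 lists hypertension as likely (over 20%), reports grade 4 cases and end-organ damage, and places its occurrence at doses of 20 mg and higher. This trial starts at 20 mg, and the chart allows restart at the same dose. Section 2.2 says hypertension was present in most patients who developed posterior leukoencephalopathy. Section 7 lists hypertension and hypertensive crisis among the toxicities of prednisone, which the second part of the trial adds.

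There is also a point of conduct. If two investigators can read sections 5 and 5.1 differently, the same event may lead to restart under one and to continued hold or discontinuation under the other.

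**Working it through.** No statistical figure bears on this point, so the check sets the passages side by side.

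**Step 1: which pressures each limit names.**

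| Place | Systolic (mm Hg) | Diastolic (mm Hg) |
|---|---|---|
| 3.1.13, enrolment | below 140 | below 90 |
| 4.2.1, contact physician (two successive readings) | 140 or more | 90 or more |
| Appendix C, contact nurse (twice in a row) | above 150 | above 90 |
| 4.2.1 and Appendix C, seek medical advice | above 180 | above 105 |
| 5.1, grade 1, first alternative | none | rise of more than 20 |
| 5.1, grade 1, second alternative | above 150 | above 100 |
| 5.1, grade 3 definition | none | none |
| 5.1, grade 3 restart | **none** | 100 or less |

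**Step 2: apply the restart condition.** Take a patient under a grade 3 hold, symptoms resolved, at 185/95.
- Symptoms resolved: yes.
- Diastolic 95 ≤ 100: yes. The chart's condition is met.
- Systolic 185 > 180: yes. The medical-advice limit is exceeded.

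The same holds for every symptom-free reading with systolic above 180 and diastolic at or below 100.

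**Step 3: locate the mismatch.** The diastolic restart value lies below the diastolic advice limit (105 − 100 = 5 mm Hg), so those two rules fit together. The mismatch is on systolic pressure alone.

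**Step 4: see whether section 5 closes the gap.** There are two readings.
- *The exception covers dose reduction only.* The general hold then still applies. A patient at 185/95 is not at baseline, since enrolment required a pressure under 140/90, and a persistent rise needing several drugs is not grade 1. He would stay on hold. But section 5 and the chart then state different end points for the same hold. Grade 3 is also defined by drug need, so a patient controlled on several added agents has not clearly returned to grade 1, while the chart allows him to restart.
- *The exception sends the whole event to the chart.* The chart then governs and has no systolic condition.

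The text does not choose. The first reading leaves two rules in conflict; the second leaves the gap.

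**Step 5: look for another safeguard.** The note under the chart ties decisions to hold or decrease the dose to clinic readings and does not mention restart. The stability that ends the 2-day checks is not defined by a pressure.

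**The case against.** The strongest reply is that nothing makes anyone restart at 185/95. The chart sets a minimum condition and leaves restart to the investigator, who must also add agents and have the pressure checked every 2 days. The 180/105 limit tells a patient when to call, and section 4.2.1 then points to 5.1 for management. The steps run in sequence, so one reading can prompt a call and also meet one condition of a discretionary restart. On one reading of section 5, the general hold keeps such a patient off the drug.

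Much of this stands. It rules out several stronger readings that a reader might infer:
- *That the protocol directs restart at a dangerous pressure.* It permits restart at discretion.
- *That two dosing rules collide at 180.* The 180/105 limit is not a dosing rule, and only Appendix C calls for advice at once.
- *That the restart cell is the protocol's only diastolic-only limit.* The grade 1 definition has a diastolic-only alternative beside "or to >150/100 if previously WNL".
- *That the grading misses such a patient altogether.* If he needs more intensive therapy he is grade 3 and the hold row applies; a hypertensive crisis is grade 4.
- *That the row on control after restart repeats the omission.* Only a fragment naming diastolic pressure can be read in the text at hand, and nothing here rests on it.

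What the reply does not remove is that the discretion is bounded on diastolic but not on systolic pressure, and that the protective reading of section 5 is only one of two.

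**Conclusion.** The point holds as a gap together with an ambiguity. The legible grade 3 cell has no systolic condition, so it can be met on a reading above the protocol's own medical-advice limit, and section 5 does not say whether its general hold or the chart decides.

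The overlap is every symptom-free reading with systolic above 180 and diastolic at or below 100. The documents give no frequency of such readings, so the number of patients cannot be stated. The conclusion assumes that the grade 3 cell is complete as printed. It says nothing about which criterion is clinically right. The gap bears on patient safety and is cheap to close, so it merits an amendment.

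**What to change.** The sponsor's physicians should reconcile section 4.2.1, the general grade 3 rule in section 5, the chart and grade definitions in section 5.1, and the Appendix C instructions. The amended text should state:
- which hold and restart criterion governs grade 3 hypertension, and whether the section 5 exception covers the hold, the dose reduction or both;
- how that criterion relates to the systolic limits the protocol already uses.

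No value or clinical rule is proposed here; that choice belongs to the sponsor's physicians.

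The cost is a short amendment. Both pressures are already recorded at clinic visits and in the diary, so no new measurement is needed. Depending on the criterion chosen, some holds may last longer. They stay within the existing 21-day maximum, but a longer hold brings a patient nearer to the point at which he is taken off study.
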